Participants randomized to treatment with MET will start at a recommended dose of 500 mg orally at night and slowly titrated in 2-week intervals to ensure that each patient achieves maximum insulin-sensitizing effects of the drug while minimizing the chance of side effects (see Table 1). We selected 50kg as the weight at which we felt comfortable increasing to a maximum total daily dose of 2000mg (1000mg twice daily). These youth will be at a low-end adult-comparable weight. We anticipate that most participants  $\geq$ 10 years old will be  $>50$ kg, which is the 95%ile for weight for 10-year-olds of both sexes. Children  $<50$ kg, likely those patients  $<10$  years, will have a reduced maximum daily dose of 1500mg. If

patients exhibit untoward gastrointestinal side effects while taking MET, clinicians will have the option to switch to an equivalent dose of the once-daily extended-release form of MET, which may alleviate side effects. If a patient does not tolerate a specific dose, the clinician will also have the option of reducing that dose by 500mg/day to a minimum recommended daily dose of 500mg twice daily. At Week 8, the dose for the <50kg group may be titrated to the maximum of 2000mg/day (1000mg twice daily) if tolerated and strategy, in general, MET will be at steady-state target levels well before key outcomes are assessed at Month 6. We will also recommend that MET be taken with food to minimize side effects. If a participant's BMI percentile <5% (=underweight) his/her treatment with MET will be discontinued. Although the risk of low vitamin B12 while taking MET is associated with age > 50 years and having type II diabetes, we will monitor B12 levels and a CBC throughout study participation.

Clinicians and patients must be willing to be randomized to either treatment arm. However, the clinician may choose to initiate or continue (for those on a subtherapeutic dose) metformin at their clinical discretion regardless of randomization following a recommended initial 3 month period of treatment. These patients' data will be considered in a different analytic group regardless of randomization.

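### The protocol states two different maximum daily metformin doses for children under 50 kg, and sites cannot tell whether going above 1500 mg is permitted

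*Combined protocol and SAP*

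**What the plan says.** The metformin dosing text follows the Schedule of Events table in the Study Schedule and Treatment section. It makes three statements about the dose ceiling and body weight.

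- The reason for the cut-off: "We selected 50kg as the weight at which we felt comfortable increasing to a maximum total daily dose of 2000mg".
- The ceiling for lighter children, described as probably those younger than 10 years: they "will have a reduced maximum daily dose of 1500mg".
- A later step for the same children: "At Week 8, the dose for the <50kg group may be titrated to the maximum of 2000mg/day (1000mg twice daily) if tolerated".

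Table 1 (Metformin Titration) gives morning and evening doses for Weeks 1 to 8 in two weight columns. The under-50 kg column reaches 500/1000 mg in Week 5 and stays there through Week 8. The entry 1000/1000 mg appears only in the column for 50 kg and above, in Weeks 7 and 8.

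The schedule is presented as advice: participants "will start at a recommended dose of 500 mg orally at night", and clinicians may reduce the dose or change to the extended-release form if it is not tolerated.

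**The concern.** The word maximum is attached to two different figures for one weight group, a few lines apart. The first figure has no time limit and is explained by body weight. The second lifts the lighter children to the ceiling of the heavier ones, and no reason is given for dropping the weight criterion at that point.

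At stake is the clarity of a dose ceiling for the smallest participants, which is a safety instruction. It also bears on how well the intervention is defined. About 40 community sites are to work from this text. The exclusion criteria refer to intolerance during the recommended titration schedule, and the Protection Against Risks section says that site staff will be trained on the recommended dosing. Each of these presumes a single schedule. If the ceiling is unclear, sites may apply different ones to comparable children. Week 8 comes well before the Month 6 assessment, so any such difference could already be present at both primary time points.

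**Working it through.** No power or sample-size calculation applies. The check is to add up the Table 1 doses and set the statements side by side.

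**Inputs.** Table 1, and the dosing text in Study Schedule and Treatment.

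**Step 1: reproduce the first ceiling.** Under-50 kg column, Weeks 5 to 8: 500 + 1000 = 1500 mg/day. This is the highest entry in the column, and it matches the first stated maximum.

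**Step 2: look for the second ceiling.** A total of 1000 + 1000 = 2000 mg/day occurs only in the column for 50 kg and above, Weeks 7 and 8. It is nowhere in the under-50 kg column, whose Week 8 entry is still 1500 mg/day.

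**Step 3: size of the discrepancy.** 2000 − 1500 = 500 mg/day, and 500/1500 = 0.33, so the second maximum is 33% above the first.

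**Step 4: compare the two weight groups.**

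| Source | Under 50 kg | 50 kg and above | Difference |
|---|---|---|---|
| Table 1, Week 8 | 1500 mg/day | 2000 mg/day | 500 |
| Text, first statement and cut-off rationale | maximum 1500 mg/day, no time limit | maximum 2000 mg/day | 500 |
| Text, Week 8 statement | maximum 2000 mg/day, optional, if tolerated | maximum 2000 mg/day | 0 |

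Table 1, the first ceiling and the rationale agree with one another. The Week 8 statement stands apart from all three, because under it the reduced maximum is no longer reduced.

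**Step 5: look for a resolution elsewhere.** The eligibility criteria, the risk section and the training description do not restate or qualify either figure for this weight group.

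**Step 6: read the Week 8 sentence to its end.** After the tolerability condition a conjunction announces something further, but the text runs straight into an unrelated clause about steady-state levels before Month 6. A second condition may have stood there. Whether it was lost in the source or when the PDF was read cannot be settled from the available text, so the gap is not counted as an error in the plan. What remains still states a second maximum.

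**The case against.** The best defence is a sequential reading: 1500 mg/day is the ceiling during the tabulated eight-week titration, and 2000 mg/day is an optional step once the table ends. The wording gives this some support, since the later sentence is tied to Week 8, is permissive, and depends on tolerability. On that reading Table 1 does not conflict, because it stops where the option begins. The reading is possible, but the protocol does not state it. The 1500 mg ceiling is not called interim, and the reason for the cut-off is body weight, not time on drug. Missing words in the Week 8 sentence could have limited the step or explained it, which lowers certainty about what was intended.

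A reader might infer that the protocol gives sites incompatible orders. It does not. Because the step is optional, a site that stays at 1500 mg/day complies with both statements, and the lower limit holds during the tabulated weeks on either reading. Only permission to go higher is in doubt.

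It is also fair to say that dosing varies by design in this pragmatic trial. The schedule is recommended, treatment may be stopped at any time, departures are recorded, and study endocrinologists are available to answer site questions. This softens the consequence. It does not supply the missing answer, since a recommendation still has to be a single one.

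**Conclusion.** The concern stands as an internal inconsistency in the description of the intervention. For children under 50 kg the protocol gives two maximum daily doses that differ by 500 mg (33%), and the higher one removes the weight-based distinction from Week 8 onward. Sites cannot tell from the text whether an increase above 1500 mg/day is permitted in this group. The conclusion rests on the text as available, with the Week 8 sentence possibly incomplete.

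Three stronger conclusions are tempting and are not supported:

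- **Harm.** No figure in the documents shows harm from the discrepancy. The background reports good tolerability at up to 2000 mg/day in studies of youth aged 8 to 18, though not specifically in those under 50 kg.
- **Bias in the primary result.** The number of participants under 50 kg is not given, and no effect on the BMI z-score analysis has been shown.
- **A dose-per-kilogram contrast.** The protocol doses by weight band. A child of exactly 50 kg belongs to the upper band, where there is no conflict, and no weight distribution is given for the lower band. The 500 mg/day difference is all that can be supported.

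The point still needs correction before sites rely on the text, because it is a dose ceiling for the youngest participants and the remedy is cheap.

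**What to change.** The sponsor should reconcile the two statements in the dosing text with each other, with the stated reason for the 50 kg cut-off, and with Table 1, so that one ceiling and one titration schedule apply to children under 50 kg. If a sequential scheme was intended, the text and the table should both say so. The Week 8 sentence should be checked against the source document and completed if words are missing. The same wording should then go into the site training material. Which figure is right is for the sponsor and its clinical advisers to decide, and none is proposed here.

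The cost is a protocol clarification, a corrected table or table note if needed, and a notice to sites. The sample size, the randomization and the analysis plan do not change.

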#### **A. SPECIFIC AIMS**

The specific aim of this study is to address the significant gap in the evidence base for metformin (MET) use in overweight and obese youth with Bipolar Spectrum Disorders (BSD).

The overall objective of this prospective, large, PRAGMATIC randomized trial is to study the impact of MET and healthy lifestyle intervention (LIFE) vs. LIFE alone on patient-centered outcomes of body weight, Second Generation Antipsychotics (SGA) adherence and satisfaction, psychiatric symptom burden (e.g. mood/anxiety), and quality of life (QoL). We will also examine metabolic outcomes.

**Specific Aim 1:** Assess the overall and subgroup-specific impact of MET+LIFE versus LIFE alone on short- (6mo) and long-term (24mo) **weight and metabolic health** in overweight and obese youth with BSD.

**H1.1:** Overall, assignment to treatment with MET will abrogate more weight gain and lead to fewer adverse metabolic outcomes than LIFE alone at 6 and 24 months.

**H1.2:** (Heterogeneity of Treatment Effects [HTE]): MET's effectiveness at abrogating weight gain and components of metabolic syndrome will vary with respect to the following factors (see Patient Population and Background for rationale and prior data): 1) Change in BMI z-score from SGA initiation to baseline (in patients already receiving SGA treatment); 2) Prior exposure to and duration of SGA treatment; 3) Baseline BMI z- score; 4) Baseline psychotropic weight burden (in SGA non-naïve patients; as defined in Measures below); 5) BSD as diagnosed by a structured interview; 6) Age; 7) Type of insurance (public/private); 8) Ethnicity (Hispanic/Non); 9) Baseline insulin resistance (HOMA-IR); 10) Race (African-American (AA) vs non-AA).

**Specific Aim 2:** Assess the overall and subgroup-specific impact of MET+LIFE vs. LIFE alone on short- (6mo) and long-term (24mo) **SGA adherence and treatment satisfaction**, including assessment of how these effects may be mediated by MET effects on weight gain.

**H2.1:** Overall, assignment to treatment with MET will lead to better SGA adherence and greater treatment satisfaction than LIFE alone after both 6 and 24 months.

**H2.2:** (HTE): MET effectiveness with regard to SGA adherence will vary with respect to: 1) Baseline weight acceptability; 2) Baseline psychotropic medication treatment acceptability; 3) Type of insurance (public/private).

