**H2.3:** The overall effects of MET treatment on SGA adherence will be mediated by degree of weight abrogation, and this relationship will be stronger among girls than boys. We anticipate a possibly complex relationship between abrogation of weight gain (associated with MET) and SGA adherence, because weight gain may also be avoided via SGA non-adherence (at the probable cost of sub-optimal psychiatric outcomes; see Specific Aim 3). A statistical framework (marginal structural models) to accommodate this possibility is described in the Statistical Analysis Plan.

**Specific Aim 3:** Assess the overall and subgroup-specific impact of MET+LIFE vs. LIFE alone on **psychiatric symptom burden, psychotropic treatment changes, and overall and weight-related QoL**, including assessment of how these effects are mediated by MET effects on weight gain and SGA adherence.

**H3.1:** Overall, assignment to treatment with MET will be associated with lower psychiatric symptom burden, decreased risk for symptom-driven treatment changes, and greater improvements in overall and weight-related QoL than LIFE alone at both 6 and 24 months, post-randomization.

**H3.2:** (HTE): MET effects on psychiatric symptoms will be smaller in patients who meet full DSM criteria for a BSD.

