### **STUDY SCHEDULE AND TREATMENT**

Since MOBILITY is a pragmatic study, we will collect the above information, when possible, and in conjunction with patients' clinical visits. We will allow for data collection approximately monthly for the first three months, followed by every three months thereafter, for a total duration of 24 months. However, these visits and timeline are just guidelines. Data will be collected through information acquired during clinical visits. There is no minimum number of visits required for patients to continue to participate in MOBILITY and have their data collected. However, sites should not schedule patient appointments exclusively to conduct study specific visits or procedures. Therefore, it is anticipated that **not all study visits or procedures will be completed for every patient. However, we will emphasize the importance of collecting Month 6 and 24 data since those are primary outcomes.** Labs tests that are recommended in the Schedule of Events are based upon standard clinical practice guidelines, but will not be required for continuation in the study.

Each site will have a copy of the MOBILITY Projected Visit Dates Spreadsheet (also found on the website: MOBILITYstudy.org). The site coordinator will enter the patient's baseline visit date where indicated, and the recommended visit schedules will auto-populate. However, once patients are randomized at baseline, MOBILITY is primarily an observational pragmatic study, therefore, data will be collected only at clinical appointments.

**Screening/Baseline Procedures:** At screening and following informed consent/assent and review of initial study criteria, we will obtain demographic and clinical information as follows:

Demographic and Clinical Characteristics: Site staff will record patients' date of birth, sex, type of insurance, contact information, and prior type and duration of psychiatric treatments. Patients will report current daily nicotine intake (packs/day) and whether they currently use other drugs (checking all that apply from a list of common drugs). Data on treatments and substance use will also be collected at six-

month intervals.

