The basic model for outcomes will be a GLMM with change from baseline to either 6- or 24- months as the dependent variable. Independent variables will include fixed-effect terms for randomized treatment group (MET), baseline value of the outcome, and random site effects. For HTE analyses, a baseline value-by-MET interaction (to assess HTE due to baseline status) will be included, and for particular domains additional continuous or categorical covariates and treatment-by-covariate interaction terms will be added to assess HTE. Outcomes within each domain will share the same set of HTE terms, specified in the Specific Aims. Because the subgroups are in general correlated (e.g., duration of SGA treatment, weight gain history and psychotropic weight burden will be correlated with baseline BMI), we will include multiple first-order HTE terms simultaneously (to assess heterogeneity independently attributable to each moderator), but will also fit separate models for each term to gauge the impact of this correlation on our conclusions. Higher-order treatment-by-covariate interactions will not be included a priori, but will be explored with rigorous adjustment for multiple testing, using step-down testing (removing highest-order interaction terms first) or information criteria based on penalized likelihoods to guide model selection.

**Marginal Structural Modeling for Causal Inference:** SA1 concerns the overall and sub-group specific effects of MET on abrogation of weight gain (with changes in BMI z-score from baseline as outcomes) and metabolic health, particularly metabolic syndrome and its component criteria. BMI and adherence measures are obtained at all study visits, so our models for these measures will use all available observations by treating the longitudinal series of changes in these variables and SGA treatment as dynamically dependent on each other. We will use marginal structural models to address this bi-directional dependence, computing the probability of SGA treatment regimen change at each visit within weight gain treatment regimen groups and using appropriately normalized versions of the inverse of the probability as the stabilized weights.

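### Moving patients who receive clinician-chosen metformin into a separate analytic group contradicts the plan's own comparison by randomised assignment

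*Combined protocol and SAP*

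**What the plan says.** Section E.a (Study Schedule and Treatment, last paragraph of the metformin text after Table 2) allows a clinician to initiate metformin, or continue it in patients on a subtherapeutic dose, "regardless of randomization following a recommended initial 3 month period of treatment". The paragraph ends: "These patients' data will be considered in a different analytic group regardless of randomization". It does not define that group. It does not say whether the group is dropped from the main comparison, merged with the metformin arm, or used only in an extra analysis.

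Other parts of the plan point to the randomised arm:

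- **Section A, H1.1:** "assignment to treatment with MET will abrogate more weight gain".
- **Section A, H2.1:** "assignment to treatment with MET will lead to better SGA adherence and greater treatment satisfaction than LIFE alone".
- **Section A, H3.1:** "assignment to treatment with MET will be associated with lower psychiatric symptom burden".
- **Section E.b, basic model:** "Independent variables will include fixed-effect terms for randomized treatment group (MET), baseline value of the outcome, and random site effects".

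On timing, Study Schedule and Treatment says "we will emphasize the importance of collecting Month 6 and 24 data since those are primary outcomes". The three-month point precedes both of these.

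**The concern.** Starting metformin off assignment happens after randomisation. If it changes a patient's analytic group, the groups compared at months 6 and 24 are no longer those formed by randomisation. Section G.a (Other potential risks) names continued weight gain above 10% as a circumstance in which a clinician may add metformin in the LIFE arm, and the primary outcome is BMI z-score. Regrouping is therefore likely, though not certain, to remove the patients gaining most from LIFE. Those left in LIFE would look better than the arm as randomised, and the metformin effect would be biased toward zero, or toward apparent harm if the true effect is small. If switching were unrelated to weight gain, this bias would not arise. In either case the analyst is left to choose between two instructions that give different answers to the primary question.

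**Working it through.** **Reading the text.** The treatment paragraph in section E.a assigns an analytic group by metformin use and sets randomisation aside. The hypotheses and the basic model define the comparison by assignment, and the model has no level or rule for a third group. Both cannot govern the same 6- and 24-month comparison. Two other places might have settled the matter:

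- Outcome Measures (section E.a) and section G.b say that data are still collected from patients who never start, or who switch. That concerns collection, not analysis.
- The marginal structural model in section E.b is built by "computing the probability of SGA treatment regimen change at each visit within weight gain treatment regimen groups". The modelled event is a change of antipsychotic, not the start of metformin.

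No text available for this review mentions intention-to-treat, analysis sets, or analysis of all patients as randomised.

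**Illustration at month 6.** The plan states no alpha, power, effect size or SD for its 1,800 patients, so there is no figure of its own to reproduce.

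Inputs from the documents:
- Difference at 24 weeks in the IMPACT study (section C): -0.088 - 0.040 = -0.128 BMI z.
- Patients per arm: 900 × 0.90 = 810, from 1:1 randomisation of 1,800 and about 90% retention (section F.f).

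Inputs assumed:
- SD of change 0.3 to 0.5. The upper value matches the pilot figure in section C if 0.27+0.5 is read as mean and SD.
- Correlation rho between early gain and month-6 change: 0.3 to 0.7.
- Share q of LIFE patients who switch: 5% to 20%.
- Switchers obtain half the metformin effect by month 6.
- Two-sided 5% test.

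*As randomised:* -0.128 × (1 - 0.5q) = -0.125, -0.122 and -0.115 at q = 5%, 10% and 20%.

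*Switchers set apart, strict selection (highest gainers first):* the LIFE mean falls by rho × SD × phi(z)/(1 - q), where z is the upper-q normal quantile. The factor phi(z)/(1 - q) is 0.109, 0.195 and 0.350. *Loose selection* (switching propensity correlated 0.5 with early gain) halves the shift.

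Example at q = 10%, rho = 0.5, SD = 0.5, strict: 0.5 × 0.5 × 0.195 = 0.049, so the estimate is -0.128 + 0.049 = -0.079, a 38% loss.

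| Share switching | Unrelated to gain | Loose | Strict (worst case) |
|---|---|---|---|
| 5% | -0.128 | -0.123 to -0.109 | -0.118 to -0.090 |
| 10% | -0.128 | -0.119 to -0.094 | -0.110 to -0.060 |
| 20% | -0.128 | -0.112 to -0.067 | -0.097 to -0.005 |

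Each range runs from rho 0.3, SD 0.3 to rho 0.7, SD 0.5.

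*Switchers merged with metformin instead:* at 10%, -0.106 to -0.060 (loose) or -0.090 to +0.002 (strict).

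*No true effect, switchers set apart:* the chance of a significant result against metformin is Phi(shift/SE - 1.96), with SE = SD × sqrt(1/810 + 1/(810(1 - q))). At q = 10%, SE/SD = 0.051.
- Loose, rho 0.3: shift/SD = 0.5 × 0.3 × 0.195 = 0.029, giving 8%.
- Loose, rho 0.7: shift/SD = 0.068, giving 27%.
- Strict: 21% to 76%.
- Loose at 5% switching: 5% to 11%.

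Simulation, which allows for the reduced spread left in LIFE, gave 9% to 28% (loose) and 20% to 80% (strict) at 10%. The reference value as randomised is 2.5%.

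*Power for a true -0.128, SD 0.5, set apart:* 96% to 99% under loose selection at 10%; 88% (strict, 10%, rho 0.5) and 38% (strict, 20%, rho 0.5) in simulation.

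**The case against.** The strongest reply is that the sentence is undefined rather than contradictory. It sits in a treatment section and does not expressly say that patients leave the main comparison. The analysis section names the randomised group, so an additional as-treated grouping beside the basic model would fit everything else. That reading is possible, and if the basic model governs and includes everyone, the randomised comparison survives. But it is stated nowhere, and the sentence itself sets randomisation aside.

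The marginal structural model also refers to weight gain treatment regimen groups, which may be where metformin actually received enters. The phrase is ambiguous, and the probability being modelled is still that of an antipsychotic change.

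Several limits stand:

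- The text between sections C and E was not available, so the absence of an as-randomised statement is claimed only for what was read.
- Some patients covered by the rule may already have been on a subtherapeutic dose at entry. Regrouping them need not follow the outcome.
- The calculations regroup LIFE patients only, whereas the rule applies to both arms.
- The documents give no switching rate, correlation or selection rule. With a three-month wait, 20% switching in strict order of weight gain by month 6 is an extreme corner.

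**Conclusion.** The concern holds and must be fixed: as written, the rule contradicts the hypotheses and the basic model on who belongs in the primary comparison. That conclusion is textual and depends on no assumed number.

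The size does depend on assumptions. Under loose selection with up to 10% switching, a true difference of -0.128 would still be detected with power of 96% or more, so the harm is mainly to the estimate (4% to 27% lost) and to error control when there is no effect. Strict selection is a worst case, in which nearly all of the effect can vanish at 20% switching. If switching is unrelated to weight gain, the month-6 estimate is not biased. Month 24 was not computed because the documents give no usable 24-month effect or SD; patients have longer to switch by then.

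**What to change.** Reconcile the section E.a paragraph with section A and section E.b. Replace its last sentence with wording such as: *The 6- and 24-month comparisons for H1.1, H2.1 and H3.1 include every randomised patient in the assigned arm, whatever metformin is received. Off-assignment metformin is recorded with its start date and reported by arm. The separate analytic group is used only in supplementary analyses, for example with inverse-probability weighting for metformin initiation.* Repeat the first of these sentences beside the basic model in section E.b.

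Clinicians' freedom to treat, eligibility and safety criteria are unchanged. The medication list is already scheduled at every visit in Table 2; the start date is a small addition and may be incomplete when visits are missed or another clinician prescribes. The wording does not deal with missing month-6 or month-24 values, which need their own rule.

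The statistical cost is dilution: 2.5% to 10% of the effect at 5% to 20% switching if switchers gain half the benefit (0.5 × q). Even if 30% switched and gained all of it, the difference would be 0.128 × 0.70 = 0.090, with 95% power at SD 0.5 and 810 per arm. That dilution is part of the effect of assignment, which is what the hypotheses ask for.
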